6.2.2 Efficacy Endpoint: DCR

Disease Control Rate (DCR) is defined as total number of patients with confirmed responses of either CR, PR, or stable disease as determined by the investigator per RECIST v1.1, divided by the total number of patients who are evaluable for a response.

Estimate of DCR and corresponding 2-sided exact 90% CI using the Clopper-Pearson method will be provided by treatment and overall. The Clopper-Pearson exact 90% CIs will be from SAS FREQ procedures with option BINOMIAL (EXACT).

6.2.3 Efficacy Endpoint: DOR

Duration of Response (DOR) is defined as the time from first response (CR or PR determined by the investigator per RECIST v1.1) that is subsequently confirmed until the onset of progressive disease or death from any cause, whichever comes first.

DOR in months will be calculated as: (date of first progression or death from any cause – date of first confirmed CR or PR + 1)/30.4375. Patients who are alive and progression-free at the time of data analysis will be censored at the time of their last assessment for tumor response. DOR for CR and PR patients will be summarized using 25th, 50th (median), and 75th percentiles with associated 2-sided 90% CIs, as well as percentage of censored observations. The median will be estimated by using the Kaplan-Meier method and corresponding 2-sided 90% CI using Brookmeyer and Crowley methodology (using log-log transformation). The detailed censoring rules are displayed in [Table 10](#).

Table 10 Censoring Rules for DOR

Situation	Outcome	Date of Progression or Censoring	Event Description/ Censoring Reason
No baseline tumor assessments	Censored	Date of first dose	No baseline tumor assessment
No baseline tumor assessment, but death within two consecutive tumor assessments period after first dose	Censored	First tumor assessment date	No baseline tumor assessment
No post-baseline tumor assessments and no death	Censored	Date of first dose	No post-baseline tumor assessment

No post-baseline tumor assessment and death after two or more consecutive missing tumor assessments from first dose	Censored	Date of first dose	No post-baseline tumor assessment
Disease progression before receiving subsequent anticancer therapy or data cutoff, whichever happens first	Event	Date of first documented progression per RECIST v1.1 (excludes clinical progression)	PD
Death without documented PD and not receiving new anticancer therapy on or before data cutoff	Event	Date of death	Death
Disease progression or death after two or more consecutive missing tumor assessments	Censored	Date of last evaluable tumor assessment prior to disease progression or death	Two or more consecutive missing tumor assessments
Subsequent anticancer therapy received without documented PD or death prior or on the same day	Censored	Date of last evaluable tumor assessment prior to the date of initiation of subsequent anticancer therapy	Started new anti-myeloma treatment before PD or death.
Alive and without progression	Censored	Date of last evaluable tumor assessment	Alive and without progression

6.2.4 Efficacy Endpoint: PFS

Progression Free Survival (PFS) defined as time from the first dose of study treatment until the first documentation by the investigator of disease progression per RECIST v1.1 or death from any cause, whichever comes first.

PFS in months will be calculated as: (date of first progression or death from any cause - date of first dose + 1)/30.4375. Patients who are alive and progression-free at the time of data analysis will be censored at the time of their last assessment for tumor response. PFS will be summarized using 25th, 50th (median), and 75th percentiles with associated 2-sided 90% CIs, as well as percentage of censored observations. The median will be estimated by using the Kaplan-Meier method and corresponding 2-sided 90% CI using Brookmeyer and Crowley methodology (using log-log transformation). The same censoring rules as DOR will be applied. See details in [Table 10](#).

6.2.5 Efficacy Endpoint: OS

Overall Survival (OS), defined as the time from the first dose of study treatment until death from any cause.

OS in months will be calculated as: (date of death from any cause - date of first dose + 1)/30.4375. Patients who are known alive as of their last known status will be censored at the date

of their last known to be alive. OS for patients will be summarized using 25th, 50th (median), and 75th percentiles with associated 2-sided 90% CIs, as well as percentage of censored observations. The median will be estimated by using the Kaplan-Meier method and corresponding 2-sided 90% CI using Brookmeyer and Crowley methodology (using log-log transformation). Number and percent of survival subject at 1 year will be estimated. The detailed censoring rules are displayed in [Table 11](#).

Table 11 Censoring Rules for OS

Situation	Outcome	Date of Progression or Censoring	Event Description/ Censoring Reason
Death before data cutoff	Event	Date of death	Death
Death after data cutoff	Censored	Date of data cutoff	Alive on or before data cutoff
No death before data cutoff	Censored	Date subject last known to be alive	Alive on or before data cutoff
Discontinued from study without death prior to data cutoff	Censored	Date subject last known to be alive	Discontinued from study

By-subject listings will be provided for target lesion, nontarget lesion, new lesion, and tumor response assessment. A by-subject listing of subsequent anti-cancer treatment will also be provided. By-subject listings for the efficacy endpoints above will also be provided.

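### SAP Table 11 censors deaths after the data cutoff at the cutoff but sets no cap on the censoring date of survivors, so OS can be raised if post-cutoff contacts are in the analysis data

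*SAP*

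**What the plan says.** SAP 6.2.5 defines OS from first dose to death from any cause. It plans Kaplan-Meier quartiles with 90% intervals, and adds "Number and percent of survival subject at 1 year will be estimated". For censoring, the text says "Patients who are known alive as of their last known status will be censored at the date" they were last known alive.

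SAP Table 11 has four rows:

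- Row 1, death before the cutoff: event at the date of death.
- Row 2, "Death after data cutoff": censored at the cutoff.
- Row 3, "No death before data cutoff": censored at "Date subject last known to be alive".
- Row 4, left the study without a death before the cutoff: censored at the same last-alive date.

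Rows 2 and 3 share the censoring reason "Alive on or before data cutoff". I found no definition of the data cutoff in the SAP and no general rule that drops later records. SAP 5.2 ends by keeping all data in the analysis, but the context there is outliers, so it does not settle the matter.

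SAP Table 10 gives the rules for duration of response (DOR), and SAP 6.2.4 reuses them for progression-free survival (PFS). One event row there reads "Disease progression before receiving subsequent anticancer therapy or data cutoff, whichever happens first". Patients without progression are censored at their last evaluable scan, again with no stated limit at the cutoff.

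**The concern.** Take two patients who are both alive at the cutoff. One dies 60 days later and is censored at the cutoff under row 2. The other is seen alive 60 days later and, under row 3, is censored at the cutoff plus 60 days. Their censoring times differ only because of what happened after the cutoff. Kaplan-Meier assumes that censoring carries no information about later outcome, and here it would.

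The rows also do not partition the patients. A post-cutoff death fits row 2 and row 3, which give different dates. A death on the cutoff date fits neither row 1 nor row 2 and, read literally, falls into row 3 as a censored case.

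The outputs affected are the OS median and 1-year survival, in small uncontrolled cohorts.

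**Working it through.** The documents give no OS median, event count or power, so there is no planned figure to reproduce. The check has two parts.

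**Direction.** Compare the literal Table 11 with a capped rule that uses the earlier of the last-alive date and the cutoff. The Kaplan-Meier estimate is S(t) = product over death times up to t of (1 − d/n), where d is the number of deaths and n the number at risk.

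- Deaths: only those before the cutoff count under either rule, so d is the same at every death time.
- At risk: the literal rule keeps some survivors under observation longer and removes nobody earlier, so n is equal or larger.
- Each factor (1 − d/n) is therefore equal or larger, and the literal curve is never below the capped curve.

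This needs no simulation. It requires only that alive dates after the cutoff are in the data.

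**Size.** This part was simulated with 400,000 patients per setting. From the documents: survival contact about every 3 months (protocol 4.4, Phase 1b). Assumed: exponential OS, uniform accrual over 12 months, cutoff at month 18, and extraction 0, 1, 3 or 6 months after the cutoff. Post-cutoff deaths are censored at the cutoff under both rules.

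| True median (months) | Lag from cutoff to extraction (months) | 1-year OS, capped | 1-year OS, literal | Difference (points) | Median, capped | Median, literal |
|---|---|---|---|---|---|---|
| 10 | 0 | 40.3% | 40.3% | 0 | 9.37 | 9.37 |
| 10 | 1 | 42.3% | 42.7% | +0.4 | 9.71 | 9.74 |
| 10 | 3 | 43.6% | 46.0% | +2.4 | 10.01 | 10.44 |
| 10 | 6 | 43.5% | 47.4% | +3.9 | 10.01 | 10.75 |
| 12 | 0 | 46.7% | 46.7% | 0 | 10.91 | 10.91 |
| 12 | 1 | 48.8% | 49.1% | +0.3 | 11.55 | 11.63 |
| 12 | 3 | 50.0% | 52.4% | +2.4 | 12.01 | 12.85 |
| 12 | 6 | 49.9% | 53.8% | +3.9 | 11.98 | 14.09 |

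At a true median of 6 months the median does not move, and 1-year OS rises from 24.9% to 27.1% (3-month lag) or from 25.0% to 28.3% (6-month lag). At a true median of 18 months, 1-year OS rises from 62.9% to 65.0% (3-month lag) or from 63.1% to 66.4% (6-month lag). The median then goes from about 18 months to not reached, but that sits at the edge of the assumed follow-up.

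**Scale.** For 30 patients and 1-year OS near 0.44, the half-width of a 90% interval, ignoring censoring, is 1.645 × sqrt(0.44 × 0.56 / 30) = 0.149, or about 15 points. Censoring makes it wider.

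**The case against.** The strongest reply is that the analysis data may be cut at the cutoff, in which case the effect is zero. The shared label "Alive on or before data cutoff" supports reading row 3 as status up to the cutoff. The protocol plans no interim analysis (9.5), and an analysis at study end would leave few later contacts. The documents give no lag between cutoff and extraction, so the 3 to 6 months used above are an assumption.

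Much of this stands, and it makes the point conditional. It does not remove it. Row 2 would be unnecessary if no record after the cutoff were kept, so the SAP allows for post-cutoff vital status in the data. The label is in the reason column, and rows 2 and 3 share it while carrying different dates. A programmer will follow the date column.

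Three narrower replies also have force:

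- Row 4 is largely moot, because patients who left before the cutoff will normally have a last-alive date before it.
- A sensible programmer would let the specific row 2 override the general row 3, although the SAP does not say so.
- OS is not among the visible primary or secondary endpoints (SAP Tables 5 to 7 and 9; the exploratory entries cannot be read), and the trial tests no hypothesis.

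A reader might infer from SAP Table 10 that PFS and DOR are biased in the same way. The documents do not show that. Table 10 has no row that censors post-cutoff progression or death at the cutoff, so the asymmetry of Table 11 is not reproduced there. Such events are simply not addressed, and no PFS or DOR calculation was made.

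**Conclusion.** The point holds in conditional form. As written, Table 11 lets the censoring date depend on what happens after the cutoff. If post-cutoff contacts are used, the OS curve can only be equal to or higher than under a common cutoff. For true medians of 10 to 12 months, the rise in 1-year OS is about 2 to 4 points at lags of 3 to 6 months, 0.3 to 0.4 points at 1 month, and zero with no post-cutoff record. Accrual, cutoff timing, lag and the exponential form are all assumed.

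A reader might infer that reported OS will be overstated outright. The documents do not support that, because they do not say that post-cutoff alive dates will be used. The comparison is also with the capped rule and not always with the truth: at lags of 0 and 1 month, out-of-date last contacts put both rules below the true 1-year OS (43.5% for a median of 10 months). The shift is modest beside an interval of at least ±15 points. The overlap of rows 2 and 3, and the gap for deaths on the cutoff date, need correcting whatever the lag.

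**What to change.** In SAP 6.2.5 and Table 11:

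- Define the data cutoff.
- Row 1: count deaths on or before the cutoff as events.
- Row 2: keep censoring at the cutoff, and state that this row takes precedence over row 3.
- Row 3, row 4 (for consistency) and the text above the table: censor at the earlier of the date last known alive and the data cutoff.

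In SAP Table 10, for consistency only, limit the last evaluable assessment to scans on or before the cutoff.

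The cost is a few words in two tables and one paragraph, and about one line of derivation code. Reported OS may be slightly lower than under the literal rule.

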#### Efficacy Analysis

Objective Response Rate (ORR) will be summarized with frequencies and percentages with 90% exact confidence interval (CI) using the binomial distribution. Progression-free survival (PFS) and overall survival (OS) will be summarized using Kaplan-Meier (KM) estimates and corresponding 90% CIs. Duration of response (DOR) will be summarized similarly as for PFS and OS for all treated subjects who achieved a confirmed CR or PR. ORR, DOR and PFS will be determined based on investigator's assessments as per RECIST v1.1.

[figure not shown]

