#### 4.4 End of Study Definition

The EOT follow-up visit approximately 100 days after the last dose of treatment on study will be considered the end of the study in Phase 1a.

In the Phase 1b portion of the study, patients will also be followed for survival by clinic visit or by telephone approximately every 3 months after the Day 100 EOT visit. Death, loss to follow-up, or withdrawal of consent of the last study subject, or study termination by the Sponsor (whichever occurs first), will be considered the end of the study in Phase 1b.

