**Table 11: Efficacy – Statistical Analyses**

Endpoint	Statistical Analysis Methods
ORR is defined as the proportion of patients whose BOR is either confirmed CR or PR per RECIST v1.1 in the population of interest.	Estimate of ORR and corresponding 2-sided exact 90% CI using the Clopper-Pearson method
BOR for a patient will be assessed per RECIST v1.1 by the investigator, unless otherwise specified.	Estimate of DCR and corresponding 2-sided exact 90% CI using the Clopper-Pearson method
DCR defined as total number of patients with confirmed responses of either CR, PR, or stable disease as determined by the investigator per RECIST v1.1, divided by the total number of patients who are evaluable for a response	
DOR DOR for a patient with a BOR of confirmed CR or PR is defined as the time between the date of first response and the date of the first objectively documented tumor progression per RECIST v1.1 or death, whichever occurs first.	Estimate by the Kaplan-Meier method and corresponding 2-sided 90% CI using Brookmeyer and Crowley methodology (using log-log transformation)
PFS PFS for a patient is defined as the time from the first dosing date to the date of first objectively documented disease progression or death due to any cause, whichever occurs first.	Estimate by the Kaplan-Meier method and corresponding 2-sided 90% CI using Brookmeyer and Crowley methodology (using log-log transformation)
OS OS for a patient is defined as the time from the first dose of study treatment until death from any cause.	Estimate by the Kaplan-Meier method and corresponding 2-sided 90% CI using Brookmeyer and Crowley methodology (using log-log transformation)

Abbreviations: BOR = best overall response; CI = confidence interval; CR = complete response; DOR = duration of response; DCR= disease control rate; PFS = progression free survival; OS = overall survival; PR = partial response; RECIST v1.1 = Response Evaluation Criteria in Solid Tumors version 1.1.

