4.6 PK-Evaluable Population

All patients who have received at least one dose of study drug and have had sufficient PK sample for the calculation of at least one PK parameter on at least one Study Day.

5 General Considerations

All programming of tables, listings and figures (TLFs) will be performed using the statistical software package SAS® version 9.4 or higher

Unless otherwise noted, continuous variables will be summarized using the number of subjects (n), mean, standard error (SE) or standard deviation (StD), median, minimum, and maximum; categorical variables will be summarized using the number and percentage of subjects in each category. Confident intervals (CI) may be included as appropriate.

Patient data listings will be based on all enrolled patients, unless specified otherwise and will be sorted by Phase, Treatment Group, Patient Identifier and Visit. Study day relative to first dose of study drug may be presented.

Unless stated otherwise, summaries will be provided separately for the following 3 groups of subjects:

- Phase 1a Monotherapy Dose Escalation/Exploration
- Phase 1b Monotherapy Dose Expansion
- Phase 1a Combination Dose Escalation/Exploration

Decimal places originally recorded in the data will be displayed in the listings. In general, the number of decimal places should not exceed 3 decimal places in the listings unless appropriate. In the summaries, values that are directly from the original value, such as range (minimum and maximum) will be reported in the original significant decimal places and not exceed 3 decimal places. Values that are calculated directly from the original value such as mean and median are reported in the original significant decimal places + 1 more decimal place. Values that are calculated from calculated values such as standard deviation and standard error will be reported in the original significant decimal places + 2 more decimal places. A full set of summary statistics will only be presented if there are 3 or more values available. If there is only 1 available value, standard deviation will be denoted as “NE” (Not Estimable). Percentages will be rounded to one decimal place. Confidence intervals (CIs) will be provided and will be rounded to 1 decimal place, unless otherwise specified, in the table and listing shell.

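### One-year overall survival is planned as a number and percent with no estimator, denominator, interval or rule for patients censored alive before 12 months

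*SAP*

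**What the plan says.** SAP 6.2.5 defines OS as time from first dose to death and plans quartiles with 90% intervals. It then states: "The median will be estimated by using the Kaplan-Meier method and corresponding 2-sided 90% CI using Brookmeyer and Crowley methodology". The one-year figure follows in a separate sentence: "Number and percent of survival subject at 1 year will be estimated". Nothing else in the section describes that figure.

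SAP Table 11 censors patients at the date last known alive when no death is recorded before cutoff. This includes the row "Discontinued from study without death prior to data cutoff".

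SAP section 5 (General Considerations) sets the default meaning of such wording: "categorical variables will be summarized using the number and percentage of subjects in each category". SAP 6.1.1 uses the same wording for disposition counts.

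The protocol synopsis, under Efficacy Analysis, says "overall survival (OS) will be summarized using Kaplan-Meier (KM) estimates and corresponding 90% CIs". Protocol Table 11 also lists Kaplan-Meier for OS, with Brookmeyer-Crowley intervals.

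**The concern.** A survival percentage at a fixed time needs a rule for patients whose follow-up stops earlier while they are alive. Kaplan-Meier supplies one, because such patients leave the risk set when they are censored. A count over a denominator has no such rule, so the programmer must choose one: treat them as not surviving, treat them as surviving, or drop them. Each choice gives a different number from the same data.

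For response rate the SAP makes that choice explicitly. SAP 6.2.1 keeps unevaluable patients in the denominator as non-responders. One-year OS has no counterpart.

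The wording also leaves the interval open. Brookmeyer-Crowley gives intervals for quantiles of survival time, such as the median. It does not give one for the survival probability at 12 months. What is at stake is a reported one-year rate that moves with the amount of early censoring and with a denominator chosen after the data are in.

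**Working it through.** The documents state no one-year OS rate, OS sample size or OS power, so there is no planned figure to reproduce. The check is what a count-and-percent would return compared with Kaplan-Meier.

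**Inputs**
- Median OS 10 months, range 6 to 15: an assumption. Ten months is a background figure for another drug in melanoma (Protocol 2.1), not a planning value for this trial.
- Cohort of 30: the Phase 1b cohort size (SAP 2.3).
- Exponential survival, with exponential dropout of 20% per year independent of survival: assumptions.

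**Closed form for median 10 months**
- Death rate λ = ln 2 / 10 = 0.0693 per month. Dropout rate μ = −ln(0.8) / 12 = 0.0186 per month.
- True 12-month OS = 0.5^(12/10) = 43.5%.
- Known alive at 12 months / N = 0.435 × 0.8 = 34.8%.
- Known dead by 12 months / N = λ/(λ+μ) × (1 − e^(−12(λ+μ))) = 0.788 × (1 − 0.348) = 51.4%.
- Not known dead / N = 100% − 51.4% = 48.6%.
- Alive / (alive + dead) = 34.8 / (34.8 + 51.4) = 40.4%.
- Censored alive before 12 months = 48.6% − 34.8% = 13.8%, or about 4 of 30 patients.

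**Simulation with n = 30, 4,000 runs, 20% per year dropout (means)**

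| Median OS (months) | True | Kaplan-Meier | Known alive / N | Not known dead / N | Alive / (alive + dead) | Censored before 12 months |
|---|---|---|---|---|---|---|
| 6 | 25.0% | 24.8% | 19.8% | 31.0% | 22.3% | 11.1% |
| 10 | 43.5% | 43.7% | 35.0% | 48.7% | 40.5% | 13.8% |
| 15 | 57.4% | 57.3% | 45.8% | 61.4% | 54.2% | 15.6% |

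The simulated values for median 10 agree with the closed form.

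**Two further cases at median 10 months**
- Data cutoff before everyone has a year of follow-up (censoring uniform over 6 to 18 months, 27.1% censored before 12 months): Kaplan-Meier 43.4%. The crude figures are 21.6% (known alive / N), 48.7% (not known dead / N) and 29.6% (alive / (alive + dead)).
- No censoring before 12 months: all four agree at 43.3%.

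The discrepancy therefore comes entirely from censoring before one year and from the unstated denominator.

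**The case against.** The strongest reply is that the SAP never calls the figure crude. It says the figure will be estimated, in a paragraph that names Kaplan-Meier just before it and points to the censoring table just after it. The protocol, whose analyses the SAP is meant to detail, prescribes Kaplan-Meier for OS without limiting it to the median. SAP 6.2.5 also plans the 25th and 75th percentiles while naming Kaplan-Meier only for the median. With censored data those quartiles come from the same curve, so the narrow wording may be loose drafting.

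This reply stands against a stronger claim that a reader might infer, namely that the sponsor has committed to a crude proportion or has confined Kaplan-Meier to the median. The documents support neither. The reply does not close the gap. A Kaplan-Meier estimate is a probability and does not yield a number of survivors, the SAP's own convention for number and percentage is counting, and the one-year interval is unspecified on either reading.

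A reader might also infer that the one-year figure will be badly wrong in Phase 1a, because the visit "approximately 100 days after the last dose of treatment on study will be considered the end of the study in Phase 1a", and that it could not be compared with Phase 1b. The documents do not carry this:
- Section 6.2.5 has no phase restriction, but the Phase 1a exploratory entries in SAP Table 9 are blacked out and the visible Phase 1a endpoints do not include OS. Whether one-year OS is reported there cannot be confirmed.
- The documents give no treatment durations from which to work out how many survivors would be censored before a year.
- Efficacy is analysed separately by part of the study, and no comparison between phases is planned.
- Kaplan-Meier would not necessarily recover the truth in Phase 1a. Censoring there is tied to stopping treatment, which may itself be related to prognosis.

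**Conclusion.** The point holds as a specification gap with a foreseeable bad outcome. The one-year OS sentence lacks an estimator, a denominator, an interval and a censoring rule. Followed literally, it gives a crude percentage that departs from the protocol's Kaplan-Meier summary.

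Under the base illustration the crude figure would be 8.5 points too low (35.0% against 43.5%), 3.0 points too low (40.5%) or 5.2 points too high (48.7%), according to the denominator chosen. The error grows with early censoring and vanishes if nobody is censored before 12 months. These sizes depend on assumed exponential survival and independent dropout.

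The consequence for the trial is limited. Analyses are descriptive, OS is not a primary or visible secondary endpoint, and no visible decision rule uses one-year OS. The correction is still worth making, because it replaces a stated count-and-percent with a defined estimator and a valid interval.

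**What to change.** Replace the one-year sentence in SAP 6.2.5 with:

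> The Kaplan-Meier estimate of OS at 12 months with a 2-sided 90% CI (log-log transformation) will be reported, with the number at risk and the number censored before 12 months.

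If OS is also reported for Phase 1a, add a note that follow-up there ends about 100 days after the last dose, so censoring may be informative and few patients will be at risk at 12 months.

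The cost is one SAP sentence, plus the note if needed. The survival procedure already planned for the median produces the estimate and its interval. No new data are collected, and the change brings the SAP into line with the protocol.
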